The primary outcome is the length of labor from epidural catheter insertion until delivery. Secondary outcomes include mode of delivery, maternal satisfaction and post-delivery complications. A power analysis was determined using historical data from epidural analgesia studies at FMC, recent FMC length of labor statistics, and estimations on length of labor reductions from the Banner Health report. To detect a 13% change in length of labor between groups with an estimated standard deviation of 46% from average length of labor (historical FMC mean =/- SD from epidural insertion to delivery is 325+/-150min), a minimum sample size of 101 per group is needed to provide a power of 0.8 and alpha of 0.05. We will enroll up to a total of 240 subjects (120 per group for 2 groups) in anticipation of potential exclusions. The study will conclude when 202 evaluable patients have completed the study.

Implications:

If peanut-shaped birthing balls improve labor outcomes without complications, practice protocols will be revised to include the routine use of them during labor in the Women's Center and possibly throughout all Novant birthing facilities. Further, publication of the results from this study will potentially affect public health policies.

Risks:

Epidural and CSE analgesia are commonly used (85%) in laboring patients at FMC (approximately 50-50 ratio). All of the usual risks for CSE labor analgesia apply including: inadequate anesthesia/analgesia, post dural puncture headache, backache, pruritus, nausea/vomiting, hypotension, as well as other very rare risks of respiratory depression, nerve injury, hematoma, infection and seizures. Although the Banner Health reports suggests that no patient experienced complications, we theorize that there is a small risk that use of the peanut-shaped birthing balls may increase the incidence of hip, pelvis or back discomfort following delivery. Patients will receive informed consent and will be treated as usual for any complications throughout labor and following delivery. All patients will be administered routine CSE medications throughout labor.

Benefits:

The results of this study may provide us a better understanding of the role of pelvic widening on labor outcomes.

Human Subjects Protection:

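### The stated 101 women per group gives about 51% power, not 80%, for the 13% change in length of labor that the trial is designed to detect

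*Combined protocol and SAP*

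**What the plan says.** The Statistics and Analysis section defines the endpoint: "The primary outcome is the length of labor from epidural catheter insertion until delivery". The power statement gives its inputs as "To detect a 13% change in length of labor between groups with an estimated standard deviation of 46% from average length of labor", and supports the SD with local data: "historical FMC mean =/- SD from epidural insertion to delivery is 325+/-150min". It concludes that "a minimum sample size of 101 per group is needed to provide a power of 0.8 and alpha of 0.05".

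Enrollment and stopping follow from that number: "We will enroll up to a total of 240 subjects (120 per group for 2 groups) in anticipation of potential exclusions", and "The study will conclude when 202 evaluable patients have completed the study".

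The Method section randomizes individual women to labor with or without the ball. There is no crossover or matching. The plan names no test for the primary outcome, does not say whether alpha is one- or two-sided, and plans no covariate adjustment.

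**The concern.** All the inputs for a sample-size check are in one paragraph, and they do not lead to 101 per group for two independent groups. The standardized effect is about 0.28, which is small, and 80% power for an effect of that size needs roughly twice as many women per group.

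The figure is the plan's only justification for its sample size, and it sets the point at which the study closes. If it is wrong, the trial stops with about an even chance of detecting its stated target while reporting 80%. A reader told that power was 80% would take a non-significant result as evidence against a 13% reduction, when such a result would often be compatible with one. The Implications section expects the findings to shape local practice and possibly public health policy, so that misreading would matter.

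**Working it through.** **Inputs, all from Statistics and Analysis.** Mean 325 min; SD 150 min (150/325 = 46.2%, consistent with the stated 46%); change 13%, i.e. 0.13 × 325 = 42.25 min; alpha 0.05; power 0.80; two groups of equal size. Assumption: two-sided alpha, since the plan does not say.

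**Standardized effect.** d = 42.25/150 = 0.2817 (or 13/46 = 0.2826 from the percentages).

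**Reproducing the plan's figure.** The one-sample or paired formula is n = (1.960 + 0.842)²/d², which gives 98.9. Solved with the t distribution it gives 100.9 (100.2 with 13/46). Both round up to 101, with 80% power at n = 101. This is the only calculation tried that returns the plan's number exactly.

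**The formula for this design.** For two independent groups, n per group = 2 × (1.960 + 0.842)²/d² = 197.9. Solved with the noncentral t it is 198.8, so 199 per group (197.5, so 198, with 13/46).

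**Power at the planned size.** The standard error of the difference at 101 per group is 150 × √(2/101) = 21.1 min. The normal approximation is Φ(42.25/21.1 − 1.960) = 0.517; the noncentral t gives 0.513 (0.515 with 13/46). If all 240 enrolled women were evaluable (120 per group), the t-based power would be 0.584 (0.587 with 13/46).

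**Difference detectable with 80% power, two-sided t-test, SD 150.**
- 101 per group: d = 0.396, so 59.4 min, or 59.4/325 = 18.3%.
- 120 per group: d = 0.363, so 54.5 min, or 16.8%.
- Conversely, 80% power for 42.25 min at 101 per group would require an SD of about 107 min (33% of the mean).

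**Other readings of the same inputs.**

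| Reading | n per group for 80% power | Power at 101 per group |
|---|---|---|
| Two-sided t-test on minutes | 199 | 0.51 |
| One-sided t-test on minutes | 157 | 0.64 |
| Log scale, CV 46%, 13% reduction, two-sided | 157 | 0.61 |
| Log scale, one-sided | 124 | below 0.80 |
| SD proportional to the mean in each arm, two-sided | 173 | below 0.80 |
| SD proportional to the mean, one-sided | 137 | below 0.80 |
| Rounding limits of 13% and 46%, two-sided | 179 to 218 | 0.48 to 0.55 |

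The log-scale SD is √ln(1 + 0.46²) = 0.438 and the effect is −ln(0.87) = 0.139. None of these two-group readings gives 101.

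**What a null result would show.** At 101 per group the 95% confidence interval has a half-width of 1.972 × 21.1 = 41.6 min, almost the whole design effect. A non-significant observed reduction anywhere from about 0.6 min (42.25 − 41.6) up to 41.6 min would leave a 42.25 min reduction inside the interval.

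**The case against.** The arithmetic itself cannot be answered. The plan's figures agree with one another (46% with 150/325, and 101 per group with 202 in total), so broken text does not explain the gap, and nothing elsewhere corrects it. The fair objections concern how much may be concluded.

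- **The origin of 101 is an inference.** The plan names no formula. The match to the one-sample or paired calculation is exact on both pairs of inputs, but other routes come close: halving the two-group number gives about 99, and an 18% effect (58.5 min) needs about 104 per group. This stands, but the error does not depend on where the number came from.
- **The 51% is conditional.** It applies to a two-sided t-test on minutes. The Background hypothesis is directional, and a one-sided test or a log scale would give 61% to 64%. This stands as a reason to label the figure; no such reading reaches 80%.
- **A null result could exclude 13%.** With a half-width of 41.6 min, an observed difference of zero or one favoring control would just exclude 42.25 min. So it is too strong to say the design could never rule out a 13% reduction. It would often fail to.
- **The motivating effect was larger.** The Background cites a 113 min reduction in the Arizona hospital study. With SD 150 min, 101 per group has over 99% power for that, and about 80% for 60 min. This is useful context, but the plan names 13% as its target and the power claim has to be true for 13%.
- **The plan does not show which element is wrong.** It could be the sample size, the effect, the SD or the power. This bears on the remedy, and is allowed for there.

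**Conclusion.** The concern holds. On the plan's own inputs, 101 per group delivers about 51% power for a 13% change rather than the stated 80%, and about 199 per group would be needed. The shortfall is 98 per group (199 − 101), roughly half the required number. Full evaluable enrollment at the 240 cap would raise power only to about 58%.

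These figures assume two independent groups of equal size, an SD of 150 min in each, and a two-sided unadjusted t-test at 0.05. The two-group structure and the SD come from the plan; the test and its sidedness are assumed. Relaxing the assumptions in the ways tabulated changes the size of the shortfall but does not remove it. Covariate adjustment, which is not planned, would have to explain about 49% of the variance in length of labor (1 − 101/198.8 = 0.49) for 101 per group to suffice. Because the figure governs both the primary comparison and the end of recruitment, it must be corrected.

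**What to change.** First, confirm the intended effect size and name the primary test: a two-sided comparison of two independent groups at alpha 0.05. Then remove the claim of 80% power for 13% and take one of two routes.

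1. **Keep the sample size and restate what it delivers.** For example: *With 101 evaluable women per group, a two-sided independent-groups t-test at alpha 0.05 has 80% power to detect a difference of about 59 min (18%), assuming an SD of 150 min; power for a 13% (42 min) difference is about 51%, or 58% with 120 evaluable per group.* This costs one corrected sentence and no extra women, but the stated power or detectable difference becomes less favorable. The 18% should be presented as what the design can detect. The documents offer no support for it as the target effect.
2. **Keep 13% at 80% power and raise the sample size.** This needs about 199 evaluable per group, 398 in total: 196 more than the planned 202, and well above the cap of 240 even before exclusions. The enrollment limit and the stopping sentence would have to change too.

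The first route is the minimum correction. If a different effect or SD was intended, the plan should state it with its source and recompute the number for two independent groups.

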Appendix:

Figure 1. Peanut-shaped birthing ball.

Figure 2. Lateral and Semi-Fowler Positioning During Labor.
